12.1.3. Vital Signs/Weight and Length

Vital sign parameters include blood pressure, respiratory rate, pulse, temperature, and pulse oximetry. Vital signs will be obtained as specified in the SoA ([Appendix 1](#)). On Day 1, vital signs will be continuously monitored throughout the gene replacement therapy infusion and recorded pre-dose and every 15 (\pm 5) minutes from the start of the infusion for the first 4 hours after the start of infusion, and then every hour (\pm 15 minutes) until 24 hours after the start of infusion. Temperature will be recorded pre- and post-infusion.

Weight and length will be measured at each trial visit as specified in the SoA ([Appendix 1](#)). On Day 1, weight and length will be measured pre-dose.

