4.6.2. Vital Signs

Length, weight, blood pressure, respiratory rate, pulse, body temperature, and pulse oximetry will be collected at every visit. For detailed schedule of events table, see [Table 1](#).

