6.2. Key Definitions

6.2.1. Definition of Baseline

The baseline value refers to the last non-missing measurement collected before gene therapy infusion of study drug. On Study Day 1, all assessments should be performed prior to administering the gene therapy infusion of study drug per protocol. The baseline value is therefore determined by the last non-missing measurement collected on or before the first day of study drug administration. If multiple measurements are recorded on the same day, the last measurement recorded prior to the gene therapy infusion will be used as the baseline value. If these multiple measurements occur at the same time or time is not available, then the average of these measurements (for continuous data) or the worst among these measurements (for categorical data) will be considered as the baseline value. This same baseline value will be used for the treatment and post-treatment periods.

The baseline values will be the first non-missing values collected for the control patients from the PNCR dataset.

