Due to COVID-19 pandemic, a few patients may complete the final visit (18 months of age) months outside of protocol-defined visit window. Summary tables for efficacy analysis will be created based on the visits up to month 18 of age and any data collected after month 18 of age visit to the end of study visit will be grouped into “Month 19 of age and older. Data collected through the final visit will be presented in the listings. In case, multiple record falls within “Month 19 of age and older” visit then first record will be used for analysis.

Safety data, such as laboratory results, vital signs, ECGs, and physical exams will be assessed by date and study day. For lab data collected on an unscheduled visit, the protocol defined visit windows will be applied. For change from baseline analyses the value associated with the scheduled visit will be used. Due to the visit window (± 7 days) for Day 60 visit and Day 72

visit, there is an overlap when assigning data to these two visits. Data collected between Day 53 to Day 66 will be assigned to Day 60 visit. Data collected between Day 67 to Day 79 will be assigned to Day 72 visit. For summaries of shifts from baseline and potentially significant values, all post baseline values will be considered for these analyses. Baseline for safety measures will be defined as the latest value before Day 1.

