10.4.3. Statistical Methods

Clinical laboratory test will be summarized at each visit during the treatment period. The baseline value will be the last measurement on or before the day of the infusion of study drug. This same baseline value will be used for all changes from baseline tables in the treatment period and post-treatment period. Natural history control data is not available for this evaluation.

Mean changes from baseline to End of Study/Early Termination will be summarized for each protocol-specified laboratory parameter with the baseline mean, visit mean, change from baseline mean, standard deviation, minimum, maximum, and median.

During the treatment period, laboratory data values will be categorized as low, normal, or high based on normal ranges of the laboratory used in this study. Shift tables from baseline to minimum value, maximum value, and final values during the treatment period will be created. The shift tables will cross tabulate the frequency of patients with baseline values below/within/above the normal range versus minimum/maximum/final values below/within/above the normal range.

The number and percentage of patients with post-baseline values during the treatment period meeting the specified criteria for Potentially Clinically Significant (PCS) laboratory values will be summarized. A post-baseline value must be more extreme than the baseline value to be considered a PCS finding. A listing will be provided that presents all of the lab values for the patients meeting PCS criteria during treatment Period.

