10.5. Vital Signs

Vital signs (pulse, respiration, temperature, diastolic blood pressure, body weight, systolic blood pressure, pulse oximetry) will be examined at each visit. Clinically-significant, treatment-emergent findings will be reported as adverse events.

A summary of changes from first recorded value in vital signs will be described at each visit on the safety set. In addition, vital signs results will be flagged as Potentially Clinically Significant (PCS) if they meet the pre-specified criteria. The number and percent of patients meeting each PCS criterion will be summarized starting at Day 1 and continuing through the end of study.

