10.6. ECG

10.6.1. Additional Safety Endpoint: Cardiovascular Safety Evaluations

Serial ECG data will be collected at scheduled time points and provided in an external dataset. A 12-lead ECG will also be conducted at scheduled visits. The baseline value will be latest measure prior to dosing. Mean changes from baseline, standard deviation, minimum, maximum, and median to End of Study/Early Termination visit will be summarized for HR, PR, QR, QRS, QTcF.

The central reviewer will identify abnormal ECGs that are PCS, the definitions for which are maintained outside of this document.

A listing of all PCS ECGs will be provided. Summaries of ECG data will be presented overall.

10.7. 12-Lead Holter Monitor

A Holter monitor will continuously record the patient's 12-lead ECG for a total of 72 hours from Day -1 (24 hours prior to the start of gene replacement therapy infusion) through 48 hours after the start of infusion. On Days -1 to Day 3, serial ECG data will be pulled from the Holter monitor at time points of 'pre-dose', '2 hour', '4 hour', '6 hour', '8 hour', '12 hour', '24 hour',

'36 hour' and '48 hour' post-dose and assessed by a central reviewer. The summaries of Holter monitor data will be done by the actual treatment received overall.

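### SAP 10.5 takes weight change from the first recorded value, normally Screening, against the SAP's own pre-infusion baseline, and gives length no post-baseline summary

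*SAP*

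**What the plan says.** SAP 10.5 states that "Vital signs (pulse, respiration, temperature, diastolic blood pressure, body weight, systolic blood pressure, pulse oximetry) will be examined at each visit". Body weight is in that list and length is not. The section then says that "A summary of changes from first recorded value in vital signs will be described at each visit on the safety set".

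The rest of the SAP uses a different reference. The glossary entry for baseline gives vital signs as one of its examples and keeps only the latest measurement before infusion. Section 6.2.1 says "The baseline value is therefore determined by the last non-missing measurement collected on or before the first day of study drug administration", and 6.4.1 says "Baseline for safety measures will be defined as the latest value before Day 1". The laboratory section (10.4.3) follows the same idea: "The baseline value will be the last measurement on or before the day of the infusion of study drug". So does the ECG section (10.6.1): "The baseline value will be latest measure prior to dosing". Protocol 14.3.1 sets the last non-missing value on or before the infusion day as the default. SAP 13, which lists changes from the protocol, records only the efficacy completers definition.

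The schedules of assessments in both documents place weight and length at Screening, Day -1 and Day 1. Protocol 12.1.3 adds: "On Day 1, weight and length will be measured pre-dose".

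For length, SAP 4.3 lists weight and length measurements among the safety endpoints, and 4.6.2 says "Length, weight, blood pressure, respiratory rate, pulse, body temperature, and pulse oximetry will be collected at every visit". Head circumference is handled in 10.8, as observed values and change from baseline.

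**The concern.** A post-dose change in weight is meant to describe what happened after the infusion. If the reference is the Screening value, each post-dose change also contains the growth between Screening and dosing, and that stretch differs from infant to infant. The effect is largest at the early visits, when infants are on glucocorticoid under Protocol 9.2.1. An infant who gained nothing after dosing could still show a positive change.

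The omission of length is a separate matter. A measure that the SAP names as a safety endpoint and collects at every visit has no stated post-baseline analysis. Section 7.2 covers birth length only.

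What is at stake is the clarity of the safety tables. No harm is shown.

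**Working it through.** **Which value comes first.** Weight has three scheduled pre-dose measurements: Screening, Day -1 and Day 1. The first recorded is therefore normally Screening, and the last is normally Day 1 pre-dose. The two rules point to opposite ends of the pre-dose record.

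**Interval covered by the change.** The inputs are the Screening window, Day -30 to -2 (Protocol 7.1), and the nominal visit days. Visit windows are ignored. The protocol's abbreviation list defines Day -1 and Day 1 as the adjacent 24-hour intervals before and after the start of infusion, so there is no Day 0. Day -k is then k days before Day 1, and Study Day d is d - 1 days after it.

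- Days from Day 1 to the visit = d - 1
- Days from Screening to the visit = (d - 1) + k, with k from 2 to 30
- Pre-dose share = k / (d - 1 + k)

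| Visit | From Day 1 | From Screening | Pre-dose share |
|---|---|---|---|
| Day 30 | 29 | 31 to 59 | 2/31 = 6.5% to 30/59 = 50.8% |
| Month 3 (Day 90) | 89 | 91 to 119 | 2/91 = 2.2% to 30/119 = 25.2% |
| Month 6 (Day 180) | 179 | 181 to 209 | 2/181 = 1.1% to 30/209 = 14.4% |
| Month 12 (Day 360) | 359 | 361 to 389 | 2/361 = 0.6% to 30/389 = 7.7% |

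The SAP glossary's date formula for study day makes the gap one day longer, 3 to 31 days. The Day 30 share is then 3/32 = 9.4% to 31/60 = 51.7%, which does not alter the picture.

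**Baseline wording.** Section 6.2.1 admits a Day 1 pre-dose value and 6.4.1 stops before Day 1. For weight this is a difference of about one day. Both conflict with the first recorded value.

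**Age spread at one visit (relevant only to the z-score suggestion).** Infants are dosed before 180 days of age. Screening ends at Day -2, so the youngest possible age at dosing is about 2 days. Age at a dose-anchored visit is age at dosing + d - 1, kept while below 14 × 30 = 420 days.

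- Month 6: 2 + 179 = 181 to 179 + 179 = 358 days, a spread of 177
- Month 8 (Day 240): 2 + 239 = 241 to 179 + 239 = 418 days, a spread of 177
- Month 12: 2 + 359 = 361 to 419 days, a spread of 58

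From 14 months of age, visits are anchored to date of birth and the spread is limited to the visit windows.

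**The case against.** The strongest reply is that nothing is lost. Section 10.5 reports at each visit, and Day -1 and Day 1 are weight visits, so a literal table would carry pre-dose rows showing growth since Screening. For the same infants, the mean change at Day 30 minus the mean change at Day 1 is the mean post-dose change. That holds for means. It does not give the median, standard deviation or range of the post-dose change, all of which 6.1 specifies for continuous data.

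It can also be said that three SAP definitions outweigh one phrase, so programmers would apply the usual baseline. They may, but 10.5 is the specific instruction for this table and says otherwise. Protocol 14.3.1 is weaker support: it sits under efficacy and allows exceptions. The conflict within the SAP does not depend on it.

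The percentages are extremes. The documents give no distribution of screening gaps, and the 51% figure needs Screening at Day -30, hence an infant at least 30 days old at dosing. This stands, and the figures should be read as bounds.

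A reader might infer that slow growth would go unseen because no age- and sex-standardised scale is named in 10.5 or 10.8. The documents do not support that. Section 10.5 also plans a count of patients meeting potentially clinically significant (PCS) criteria, which are held outside the SAP, so whether a weight flag exists cannot be checked. Clinically significant findings become adverse events, and 8.3.18 applies a WHO third-percentile weight criterion at 18 months. Leaving out z-scores is a choice, and 10.8 already uses change from baseline for head circumference.

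**Conclusion.** Two defects in the text stand. Section 10.5 contradicts the SAP's own baseline for vital signs, with no declared departure, and length has no post-baseline summary. Read literally, 10.5 puts 2 to 30 days of pre-dose growth into each post-dose weight change: up to about half of the interval at Day 30, falling to at most 8% by Month 12. These bounds assume that Screening is the first recorded value, that visits fall on nominal days, and that the sentence is applied as written.

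This is a minor safety-reporting correction. It shows no harm and leaves the efficacy conclusions unaffected. The case for z-scores is only that they would help: ages at one dose-anchored visit can differ by up to about 177 days, so raw changes mix infants at different stages of normal growth.

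**What to change.** In SAP 10.5, replace the reference to the first recorded value with: *changes from baseline (last value before infusion, including Day 1 pre-dose, per 6.2.1)*. Use the same wording for safety measures in 6.4.1, and add length to the 10.5 parameter list. This costs only SAP wording and one more table parameter from data already collected.

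Optionally, in 10.5 and 10.8, summarise WHO age- and sex-specific z-scores for weight, length and head circumference by visit beside the raw values. They can be derived from date of birth, sex and the measurements on file. The downside is a little extra programming, and z-scores do not remove confounding by disease, feeding support or steroids.

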10.6. ECG

10.6.1. Additional Safety Endpoint: Cardiovascular Safety Evaluations

Serial ECG data will be collected at scheduled time points and provided in an external dataset. A 12-lead ECG will also be conducted at scheduled visits. The baseline value will be latest measure prior to dosing. Mean changes from baseline, standard deviation, minimum, maximum, and median to End of Study/Early Termination visit will be summarized for HR, PR, QR, QRS, QTcF.

The central reviewer will identify abnormal ECGs that are PCS, the definitions for which are maintained outside of this document.

A listing of all PCS ECGs will be provided. Summaries of ECG data will be presented overall.

10.7. 12-Lead Holter Monitor

A Holter monitor will continuously record the patient's 12-lead ECG for a total of 72 hours from Day -1 (24 hours prior to the start of gene replacement therapy infusion) through 48 hours after the start of infusion. On Days -1 to Day 3, serial ECG data will be pulled from the Holter monitor at time points of 'pre-dose', '2 hour', '4 hour', '6 hour', '8 hour', '12 hour', '24 hour',

'36 hour' and '48 hour' post-dose and assessed by a central reviewer. The summaries of Holter monitor data will be done by the actual treatment received overall.

10.8. Physical Examination

Treatment-emergent abnormal findings on physical exam will be tracked as adverse events. Any post-infusion abnormal physical exam findings will be listed by patient with the corresponding result on the baseline physical exam. Descriptive statistics only are planned for this data.

A listing of physical examination findings including 'Normal', 'Abnormal Not Clinically Significant', 'Abnormal Clinically Significant' and "Abnormal CS, related to underlying disease" will be provided. Additionally, "Abnormal CS, related to underlying disease" will be categorized into "Abnormal Clinically Significant" and presented in the shift table. The Shift table summarizing the shift of physical examination results ('Normal', 'Abnormal Not Clinically Significant', 'Abnormal Clinically Significant') for examination items from baseline to post-baseline visits will be presented. A table summarizing observed and change from baseline values for head circumference will be produced.

10.9. Pulmonary Exam

Patients will be assessed by a pulmonologist at the time points specified in the Schedule of Assessments on of the pulmonologist and/or investigator. Non-invasive ventilatory support equipment will be provided by AveXis, Inc. through a third-party vendor.

Pulmonary exam results will be presented in a listing.

10.10. Echocardiogram

Echocardiograms will be conducted at the time points specified in the Schedule of Assessments. Clinically significant, treatment-emergent findings (as determined locally) may be reported as AEs. A listing of echocardiogram results (abnormal/normal, etc.) and findings (left ventricle function, patent foramen ovale, or other) will be provided for all screening and post-baseline visits.

Additionally, echocardiogram data will be provided to an external cardiologist for centralized review. For any future analyses, the centrally reviewed data will be considered the primary echocardiogram source data.

Descriptive statistics for change from baseline in echocardiogram parameters, including but not limited to LV EF Single Plan 2D, will be presented at each visit, including mean, standard deviation, median, minimum, and maximum values.

10.11. Ventilatory support

The number of hours per day of non-invasive positive pressure ventilator in the intervals between each post-baseline visit will be summarized overall using descriptive statistics.

10.12. Other Safety

10.12.1. Additional Safety Endpoint: Immunologic Response

Immunoreactivity to AAV9 and hSMN will be monitored by the collection of samples at Screening, Day 7, Day 14, Day 21, and Day 30. Antibody titer levels are measured through ELISA immunoassay. Antibody titers >1:50 are considered positive for antibody response while antibody titers ≤1:50 are considered negative. The number and percent of patients responding Positive or Negative for antibody response at each time point will be summarized. Furthermore, the distribution of patients by titer level will be summarized.

Secondly, T-cell response to AAV9 and SMN will be measured by the collection of samples at Day 7 and 30 and determined through the quantification of number of Spot Forming Cells (SFC) per million Peripheral Blood Mononuclear Cells (10^6 PBMC). SFC values >100 are considered positive. T-cell response to AAV9 will be measured separately in two peptide pools. T-cell response to SMN will be measured in a single peptide pool.

The number of SFC/ 10^6 PBMC will be summarized at each sample time point. For each post-infusion time point, the number and percent of patients responding positively for T-cell response will be summarized.

10.12.2. Vector Shedding

Saliva, urine, and stool samples will be collected for vector shedding in accordance with the Schedule of Study Assessments, which includes 24 hours (Day 2) and 48 hours (Day 3) post-dose.

A listing of vector shedding will be provided.

11. HEALTH ECONOMICS

The analysis of healthcare resource utilization data may be performed upon the data availability.

12. INTERIM ANALYSES

Not applicable for this SAP.

13. CHANGE FROM ANALYSIS PLANNED IN PROTOCOL

The efficacy completers population definition in the 9 Jan 2018 version of the protocol reflects:

- All treated patients who reach 14 months of age, OR
- All treated patients who meet discontinuation criteria, discontinue the study due to an AE or death

However, for this analysis the efficacy completers analysis population will consist of:

- All treated patients who reach 14 months of age for the survival endpoint **or up to and including 18 months of age for the endpoint of achievement of functional independent sitting**, OR
- All treated patients who meet discontinuation criteria, discontinue the study due to an AE, or experience death

15. PROGRAMMING CONSIDERATIONS

See TLF documentation for details.

16. QUALITY CONTROL

[figure not shown]
Refer to Quality Control Plan for SAS programs.

17. APPENDICES

17.1. Performance Criteria for Bayley Scales of Infant and Toddler Development (Version 3) Developmental Milestones

[figure not shown]
| Developmental Milestone | |
|---|--|
| Head Control – Gross Motor Subtest Item #4 | |
| Rolls from Back to Sides – Gross Motor Subtest Item #20 | |
| Sits Without Support – Gross Motor Subtest Item #26 | |
| Stands with Assistance - Gross Motor Subtest Item #33 | |
| Crawls – Gross Motor Subtest Item #34 | |
| Pulls to Stand – Gross Motor Subtest Item #35 | |
| Walks with Assistance – Gross Motor Subtest Item #37 | |
| Stands Alone – Gross Motor Subtest Item #40 | |
| Walks Alone – Gross Motor Subtest Item #42 | |

[figure not shown]
17.2. PERFORMANCE CRITERIA FOR WORLD HEALTH ORGANIZATION (WHO) DEVELOPMENTAL MILESTONES

| Gross Motor Milestone | Performance Criteria |
|--------------------------|---|
| Sitting without support |  |
| Hands-and-knees crawling | |
| Standing with assistance | |
| Walking with assistance | |
| Standing alone | |
| Walking alone | |
| | |

WHO = World Health Organization

Source: World Health Organization Multicentre Growth Reference Trial Group

17.4. SUMMARY OF CHANGES

The section below highlights content changes represented in version 2.0 of the SAP.

Global updates made through the entire document and not specified in the list of section-specific changes below:

Minor wording and formatting updates have been made throughout the SAP in order to correct typographical errors and to align wording across sections. These changes did not change the intent of the analysis.

The approval signature page was updated to follow the latest template.

Section 2.1 was updated to remove [REDACTED] as the responsible CRO for statistical and programming support.

Section 3.3 was updated to add new developmental milestones to be consistent with protocol version 7.0.

Section 3.4 was updated to revise safety objective to be consistent with protocol version 7.0.

Section 3.5 was updated to adopt the latest study design schematic figure.

Section 3.5 was updated to adopt the latest version of schedule of assessments.

Section 3.7 was updated to use 0.025 as significant level for one-sided test in primary objective.

Section 4.2 was updated to add new developmental milestones to be consistent with protocol version 7.0.

Section 4.3 was updated to revise the safety endpoints to be consistent with protocol version 7.0.

Section 4.6.7 was updated to revise cardiovascular safety evaluations due to protocol updates

Section 5.6 was updated to revise the survival rate at month 14 of age in PNCr data.

Section 5.9 was updated to replace AveXis SOP by ICH E3 Guidelines.

Section 6.2.3 was updated to redefine the final treatment values due to COVID pandemic cases.

Section 6.3 was updated to revise the strategy to hand missing values.

Section 6.4.1 was updated to revise the visit window due to Day 44 and Day 72 visit overlap.

Section 6.5 was updated to update the timing of data cutoff/database lock and corresponding statistical analyses.

Section 6.6 was updated to change the expected the number patients enrolled in a single site.

Section 6.7 was updated to simplify the subgroups.

Section 7.4.1 was updated to add conversion to prophylactic prednisolone when other glucocorticosteroids was used.

Section 8.3 was updated to restrict analyses on ECP and revise the summary tables for data collected during COVID pandemic period.

Section 8.3.1-8.3.14 were updated to add new developmental milestones analyses.

Section 10.3.2.4 was updated to revise the categories of AESI.

Section 10.4.2 was updated to remove the PCS criteria, which will be versioned out of SAP.

Section 10.4.3 was updated to revise the criteria, which will be summarized

Section 10.5 was updated to remove the PCS criteria, which will be versioned out of SAP.

Section 10.6.1 was updated to revise the ECG summary information.

Section 10.7 was updated to add holter monitoring.

Section 10.12.1 was updated to revise the immunologic response.

Section 10.12.2 was updated to add vector shedding.
